2.3 Study design

This study is designed as a randomized, active-controlled, open label, evaluator blind, parallel group, multi-center, multi-national, Phase IV trial. Patients will be randomized 1:1 to receive febuxostat or allopurinol.

There will be approx. 35 sites in the following countries: Germany, the Netherlands, Italy, Poland, Serbia, Romania.

Study duration for individual patients will be 39 weeks. This includes a one-week run-in/screening period which can be extended to max 30 days in case of re-testing, followed by a 36 weeks treatment and a 2 weeks safety follow-up (by phone call).

The study physician responsible for randomization and drug supply handling is unblinded to study medications and therefore will not be involved in the main efficacy evaluations of each patient randomized in the study.

Conversely, the study physician/s responsible for the main efficacy evaluation (Pulse Wave Velocity) will be blind to study treatments. In addition, key efficacy variables will be performed by an independent core laboratory where the central reader will be blind to the treatment assigned to patients.

Fasting lipid levels, NTproBNP, BNP, markers of inflammation and endothelial activation/adhesion, oxidative stress parameters, eGFR, changes in urine albumin excretion as evaluated by first morning albumin/creatinine ratio will be also measured by a central laboratory.

Eligible patients will be randomized to treatment with allopurinol 100 mg or febuxostat 80 mg (1:1 ratio). Up-titration of allopurinol or febuxostat to the maximum dose permitted in the study may be performed between Week 2 and Week 10, see flow chart below for details.

A follow-up safety assessment will be performed by a phone call 2 weeks after study termination.

STATISTICAL ANALYSIS PLAN

[figure not shown]
Protocol No: MEIN/14/FEB-PWV/001 (FORWARD)

Version Number: 2.0

Date of Issue: 2018-03-16

Page 10 of 22

Trial flow chart

Notes:

	Day -30 to Week -1	Day 0	Week 2 ± 4 days	Week 12 ± 4 days	Week 24 ± 4 days	Week 36 ± 4 days	Week 38 + 3 days after
	Visit -1	Visit 0	Visit 1	Visit 2	Visit 3	Visit 4	Visit 5 Phone call
	Screening	Randomization	On Treatment Visit	On Treatment Visit	On Treatment Visit	End of Study visit	Safety Follow up
Inclusion/exclusion crit.	X						
Informed consent	X						
Randomization		X					
Medical history	X						
Concomitant medications	X	X	X	X	X	X	
Physical examination	X			X	X	X	
Vital signs (BP, HR body temperature)	X	X		X	X	X	

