Height, Body Weight, demography	X						
12-Lead ECG	X						
Pulse Wave Analysis (PWA): PWV, arterial stiffness, central blood pressure, augmentation index		X		X	X	X	
BNP, NTproBNP		X		X	X	X	

STATISTICAL ANALYSIS PLAN

Protocol No: MEIN/14/FEB-PWV/001 (FORWARD)

Version Number: 2.0

Date of Issue: 2018-03-16

Page 11 of 22

	Day -30 to Week -1	Day 0	Week 2 ± 4 days	Week 12 ± 4 days	Week 24 ± 4 days	Week 36 ± 4 days	Week 38 + 3 days after
	Visit -1	Visit 0	Visit 1	Visit 2	Visit 3	Visit 4	Visit 5 Phone call
	Screening	Randomization	On Treat- ment Visit	On Treat- ment Visit	On Treat- ment Visit	End of Study visit	Safety Follow up
Serum Uric Acid	X		X	X	X	X	
Oxidative stress parameters: MDA, MPO, Ox-LDL, PON1 and PON 2		X		X	X	X	
Markers of inflammation: hsCRP, TNF-α, plasma fi- brinogen		X		X	X	X	
Markers of endothelial activa- tion/adhesion: sVCAM, sICAM, vWF, e-selectine (selected sites)		X		X	X	X	
Fasting lipid levels	X			X	X	X	
eGFR		X		X	X	X	
Urine Albumin excretion measured as Albumin to cre- atinine ratio		X		X	X	X	
Tender and swollen joint count		X		X	X	X	
Cigarette smoking, alcohol consumption	X	X	X	X	X	X	X
Urine pregnancy test		X				X	
Safety Laboratory Tests	X			X	X	X	
IMP dispense		X	X	X	X		
IMP accountability			X	X	X	X	
Adverse events	X	X	X	X	X	X	X

NOTES: * screening period lasts up to 7 days but can be extended to max 30 days in case of re-testing of sUA. sUA can be re-tested if current sUA level is changed due to acute (transient) condition as it is not in line previous medical data as per investigator opinion and approval from the Sponsor.

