5.7.2 Secondary endpoints

All secondary efficacy variables will be analyzed based on the FAS population.

For the analysis of continuous secondary efficacy variables, the ANCOVA model with change from baseline to respective time point as a response variable and respective baseline value and treatment group as the terms in the model will be used at each time point for the parameters listed below. The LOCF method will be used for missing data imputations.

- Changes in BNP and NTproBNP values after 12, 24 and 36 weeks of treatment
- Changes in inflammation markers (hsCRP, TNF- α , sUA, and plasma fibrinogen) after 12, 24 and 36 weeks of treatment
- Changes in oxidative stress parameters [Malondialdehyde (MDA), Myeloperoxidase (MPO) Oxidized low-density lipoprotein (Ox-LDL),] after 12, 24 and 36 weeks of treatment
- Changes in lipid profile after 12, 24 and 36 weeks of treatment
- Changes in eGFR with CKD-EPI formula after 12, 24 and 36 weeks of treatment
- Changes in urine albumin excretion as evaluated by first morning urine albumin/creatinine ratio (mg/g) after 12, 24 and 36 weeks of treatment
- Pulse Wave Analysis (including modifications of PWV, arterial stiffness, central blood pressure and augmentation index) after 12, 24 and 36 weeks of treatment
- The primary parameter PWV over time (12 to 36 weeks) will be analyzed using a repeated measurement model
- Changes in endothelial activation/adhesion markers (sVCAM, sICAM, vWF, e-selectine) after 12, 24 and 36 weeks of treatment (These parameters will be evaluated in a subset of patients enrolled in selected centers only)
- Tender and swollen joint count

Logistic regression will be used to analyze the parameters below for the difference between treatment groups at each time point where the dependent variable is defined as a binary outcome (e.g. 1 if urate concentration ≤ 6 mg/dl, 0 otherwise) and treatment group and baseline urate concentration will be included as independent variables.

- Percentage of gout patients with a serum urate concentration of less than or equal to 6 mg/dl after 12, 24 and 36 weeks of treatment
- Percentage of patients above the sUA target levels at Week 12, Week 24 and Week 36 after having reached the sUA target levels at Week 2

STATISTICAL ANALYSIS PLAN

Protocol No: MEIN/14/FEB-PWV/001 (FORWARD)

Version Number: 2.0

Date of Issue: 2018-03-16

Page 19 of 22

Proportional hazards model with treatment group as covariate will be used to investigate:

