- Time to achieve sUA target levels for all patients with baseline sUA as additional covariate
- Time to achieve sUA target levels stratified for sUA levels at baseline as follows: 8.1-8.8 mg/dl, 8.9-9.6 mg/dl, 9.7-10.3 mg/dl, 10.4-11.0 mg/dl, >11 mg/dl
- Time to achieve sUA target levels for all patients and stratified for sUA levels at baseline as follows: >8 and <9 mg/dl, >9 and <10 mg/dl, ≥ 10 mg/dl will additionally be presented

In case of deviation from proportional Hazard-assumption the log-rank-test will be used instead.

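### Time to sUA target: the additional baseline strata have no place for exactly 9.0 mg/dl, and the log-rank fallback does not remedy non-proportional hazards (secondary endpoint, minor)

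*SAP*

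**What the plan says.** All the rules are in SAP section 5.7.2. The planned method is: "Proportional hazards model with treatment group as covariate will be used to investigate" three items.

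- The first is "Time to achieve sUA target levels for all patients with baseline sUA as additional covariate".
- The second is stratified by five baseline bands: "8.1-8.8 mg/dl, 8.9-9.6 mg/dl, 9.7-10.3 mg/dl, 10.4-11.0 mg/dl, >11 mg/dl".
- The third covers all patients and a second set of bands: ">8 and <9 mg/dl, >9 and <10 mg/dl, ≥ 10 mg/dl will additionally be presented".

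The section then gives the fallback: "In case of deviation from proportional Hazard-assumption the log-rank-test will be used instead". It does not say how a deviation would be judged, whether the log-rank test would be stratified, or what effect measure would go with it.

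Two facts from section 2.3 bear on this. In the trial flow chart, the row "Serum Uric Acid" is marked after randomization only at Weeks 2, 12, 24 and 36. The text also says: "Up-titration of allopurinol or febuxostat to the maximum dose permitted in the study may be performed between Week 2 and Week 10".

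**The concern.** **Strata.** The first two of the three additional bands are open at 9, so a patient at 9.0 mg/dl belongs to neither. The five-band set is written to 0.1 mg/dl, so 9.0 is an attainable value. The programmer would have to drop these patients or choose a band after seeing the data.

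**Fallback.** The rule is meant for the case where the treatment effect changes over time. The test it turns to sums the treatment difference over time with the same weights as the Cox score, so differences of opposite sign cancel. Such a change is foreseeable here. The Week 2 value comes at the start of the titration window and the Week 12 value after it, so the contrast between arms need not be the same at both visits. If it differs, the fallback can miss a real difference, and it yields a p-value with no estimate beside it.

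**Working it through.** The SAP gives no event count, hazard ratio or power for time to sUA target, so there is no figure of its own to reproduce. Every response rate below is an assumption.

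**1. Strata.** Each value from 8.1 to 13.0 in steps of 0.1 was assigned to the bands.

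- Five-band set: no value is left out, and 9.0 falls in 8.9-9.6.
- Three-band set: one value is left out, 9.0.

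The SAP gives no baseline distribution. If the 182 planned patients were spread evenly over 8.1 to 11.0 (30 values), 182/30 = 6.1 would sit at 9.0. Over 8.1 to 10.0 (20 values), the figure is 182/20 = 9.1.

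**2. Log-rank and Cox are the same contrast.** With treatment as the only covariate, the Cox score at a hazard ratio of 1 is U = Σ(d1 − D·n1/N), summed over event times. Here d1 and n1 are events and patients at risk in one arm, and D and N are the totals. This is the log-rank numerator. In 2,000 simulated trials per scenario (91 per arm, continuous times), the log-rank z had correlation 1.000 with the Cox score z. Rejection rates (log-rank / Cox Wald) were:

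- null: 5.4% / 5.3%
- proportional hazards, ratio 1.6: 82.8% / 82.7%
- crossing hazards (0.03 then 0.08 against 0.06 then 0.03 per week, changing at Week 12): 11.8% / 11.8%

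With the crossing hazards observed only at Weeks 2, 12, 24 and 36, the rates were 7.4% / 2.1%. That gap comes from the Breslow handling of heavy ties, and both are low.

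**3. How the contributions cancel.** The inputs are 85 per arm and assumed cumulative percentages at target by Weeks 2/12/24/36. Arm B leads at Week 2 in every scenario.

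- Crossing: A 30/79/87/91, B 50/73/81/85
- Catch-up without crossing: A 30/70/80/85, B 50/75/82/86
- Early lead kept: A 30/60/70/75, B 50/75/82/86

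In all three, expected events at Week 2 are 0.30 × 85 = 25.5 in A and 0.50 × 85 = 42.5 in B. So D = 68, the expected share of B is 34, and its contribution is 42.5 − 34 = +8.5. At Week 12, 59.5 (A) and 42.5 (B) remain at risk, N = 102. In the crossing case, events are 0.49 × 85 = 41.65 and 0.23 × 85 = 19.55, D = 61.2, and the contribution is 19.55 − 61.2 × 42.5/102 = 19.55 − 25.5 = −5.95. The same formula at each visit gives:

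| Scenario | Wk 2 | Wk 12 | Wk 24 | Wk 36 | Sum U |
|---|---|---|---|---|---|
| Crossing | +8.5 | −5.95 | −0.85 | −0.64 | +1.06 |
| Catch-up | +8.5 | −1.77 | −0.62 | −0.22 | +5.89 |
| Lead kept | +8.5 | +1.77 | +0.39 | +0.53 | +11.19 |

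**4. Power, by simulation.** The log-rank test with hypergeometric variance was compared with the sum of visit-specific likelihood-ratio tests, two-sided at 0.05.

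| Scenario | Log-rank | Visit-specific |
|---|---|---|
| Crossing | 7% | 88% |
| Catch-up | 27% | 62% |
| Lead kept | 69% | 59% |

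Repeat runs agree to within about 3 percentage points. Under the null, one run gave 5.3% and 6.2%. With proportional hazards the log-rank test is also the better one: 52% against 34% at a ratio of 1.4, and 66% against 47% at 1.5.

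**The case against.** The strongest defence is that the log-rank test needs no proportional hazards to be valid under the null; the simulated 5.4% bears this out. Moving from a hazard ratio that has become hard to interpret to a test of equal curves is a conventional step. This stands. A reader might infer that the fallback is an invalid test, and it is not. What it lacks is sensitivity and an estimate.

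Second, nothing in the SAP says the curves will cross. Titration makes a changing effect plausible, no more. This also stands: the 7% figure belongs to one assumed pattern, and the log-rank test is the better choice when the effect is consistent. A reader might infer that the proportional hazards model itself should go. The figures do not support that.

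Third, the SAP does not exclude a log-rank test stratified by its own bands. That is fair, but it names neither strata nor covariate, so as written the adjustment is lost.

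Fourth, section 5.7.2 already plans logistic regression of the percentage at target at Weeks 12, 24 and 36, adjusted for baseline urate. A late reversal could show there. The cover is partial, because those analyses do not compare the arms at Week 2.

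A reader might also infer that a Cox model would rank patients by where a visit fell in its ±4-day window. The SAP does not say whether actual or scheduled times are used, so this cannot be held against it.

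**Conclusion.** The point holds in two limited parts.

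**Strata.** The omission of 9.0 mg/dl is an error on the face of the text. Its reach is small. A reader might take it that these patients are lost from the analysis, but they remain in the all-patient model and in the 8.9-9.6 band. The figure of 6 to 9 patients rests on an assumed even spread and recording to 0.1.

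**Fallback.** Replacing the Cox model with the log-rank test does not address what triggers the switch. It regains no power worth the name, leaves no effect estimate and, as written, drops the baseline sUA adjustment. The identity with the Cox score test does not depend on assumed rates. The size of the loss does: it is large if the curves cross, moderate under catch-up, and reversed if an early lead is kept.

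The endpoint is secondary, and neither the primary PWV analysis nor safety is affected. Severity is minor.

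**What to change.** - Write the additional bands as >8 to <9, ≥9 to <10 and ≥10 mg/dl. No value above 8 is then left out.
- Keep the proportional hazards model as the planned analysis.
- Replace the log-rank fallback with a discrete-time (complementary log-log) model by scheduled visit (Weeks 2, 12, 24 and 36), with terms for visit, treatment, treatment-by-visit and baseline sUA.
- With it, report the cumulative percentage at target by each visit per arm, with 95% confidence intervals.

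The cost is a few lines of SAP wording and one standard model. The downside is that, when the fallback is triggered, the result is a set of visit-specific effects rather than one test, with less power if the effect is in fact consistent over time (59% against 69% in the scenario above). Changing only the fallback confines that loss to cases where non-proportionality has been declared.

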5.8 Pharmacokinetics / Pharmacodynamics

Not applicable.

5.9 Safety

All analyses will be performed for the SAF population.

5.9.1 Adverse events

Adverse events (AEs) will be coded by the CRO Safety Group according to the MedDRA thesaurus. Coding will be agreed upon with the Sponsor before database lock (cf. DMP).

Treatment-emergent adverse events (TEAE) will be analyzed, i.e. all new and worsening pre-existing adverse events occurring after first IMP administration up until end of trial. It is assumed that for each increase in intensity of an AE a new entry of the AE will be done by the investigator; hence such cases will be analyzed like different phases of the same AE.

A descriptive analysis will be performed. Global incidences along with the number of events and number of patients with events per primary system organ classes (SOC) and preferred terms (PT) will be calculated for

- All TEAE irrespective of the causality assessment
Related TEAEs (Certainly, Probably, Possibly Related and Unassessable)
- TEAEs by worst severity
- Serious TEAEs
- TEAEs without serious

STATISTICAL ANALYSIS PLAN

Protocol No: MEIN/14/FEB-PWV/001 (FORWARD)

Version Number: 2.0

Date of Issue: 2018-03-16

Page 20 of 22

This analysis comprises the following set of tables split by treatment group:

- Global incidence
- Incidences by primary system organ classes (SOC) and incidences of PT within primary SOC sorted according to the Internationally Agreed Order

Multiple counts within a PT or SOC (repeated or different included terms or changes in descriptors) will be counted only once for the calculation of incidences.

A listing of "special cases" containing subject identification, age, sex, AE descriptors, start and end of treatment will be prepared for the following types of TAEs:

- Serious adverse events (SAE)
- Adverse events which led to death
- Adverse events which led to discontinuation

All adverse events recorded since signing of the ICF will be listed in the data part of the report. Only TEAEs will be summarized in the tables.

5.9.2 Vital signs

Vital signs parameters (systolic/diastolic blood pressure, pulse, body weight, axillary body temperature) will be assessed at screening, visit 0, 2, 3 and at end of the trial.

Descriptive analyses of values and their changes from baseline will be performed.

5.9.3 Safety laboratory variables

For quantitative laboratory parameters, mean changes from baseline to the different study visits as well as to the final value will be summarized. Laboratory data values will be categorized as low, normal, or high based on normal ranges of the laboratories used in this study. Shift tables from baseline to final values will be created for each variable. The shift tables cross tabulate the frequency of patients with baseline values below/within/above the normal range versus final values below/within/above the normal range.

Frequency tables for the semi-quantitative urinalysis results will be presented by visit.

Frequency tables or listings for values classified as clinically significant by the investigator will be provided per time point if applicable.

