5 STATISTICAL ANALYSES

All statistical analyses will be performed using SAS® for Windows (Version 9.3 or later). Descriptive statistics will always be given by treatment group. For baseline and basic variables, they will also be given for the entire population. Unless otherwise noted below all analyses will be based on the FAS population.

If not stated otherwise the following standard descriptive statistics will be presented:

Descriptive statistics for continuous data

Number of subjects (N), arithmetic mean, standard deviation (SD), minimum, lower quartile, median, upper quartile and maximum will be presented. Usually mean and quartiles will have 1 decimal more, SD 2 decimals more than the original values (as given with min, max); N has no decimals. These descriptive statistics will be determined for measured values and for differences to baseline.

Descriptive statistics for categorical data

Absolute frequencies (N) and relative frequencies (%) will be presented with 0 or 1 decimal, respectively. For changes from baseline, shift tables may be generated.

Inferential statistics

If not stated otherwise all statistical tests will be performed two-sided and at a type I error probability of $\alpha=0.05$. All p-values will be rounded to three decimal places. Statistical significance will be declared if the rounded p-value will be less than 0.050. If a p-value is less than 0.001 it will be reported as "<0.001." If a p-value is greater than 0.999 it will be reported as ">0.999."

All confidence intervals (CI) will be derived two-sided and at a confidence probability of $1-\alpha = 0.95$.

Listings

All patient data will be listed by patient sorted by treatment group. Identification variables will be center number, patient number and treatment. Any derived data listed will also be stored permanently and will be calculated as outlined in section 8.1 of this SAP.

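### The laboratory shift tables in SAP 5.9.3 use only the baseline and final values, so no specified output counts quantitative values out of range at Week 12 or 24 by arm

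*SAP*

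**What the plan says.** SAP section 5.9.3 sorts laboratory values into low, normal and high and then specifies one cross-tabulation of them for quantitative variables: "Shift tables from baseline to final values will be created for each variable". Its axes are "baseline values below/within/above the normal range versus final values below/within/above the normal range". The section does not say whether the final value is the Week 36 value or the last one available.

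The flow chart in section 2.3 has the row "Safety Laboratory Tests X X X X". The four marks stand under screening, Week 12, Week 24 and Week 36, so three samples are post-baseline.

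The other laboratory outputs in 5.9.3 are:
- for quantitative parameters, "mean changes from baseline to the different study visits as well as to the final value will be summarized";
- for urinalysis, "Frequency tables for the semi-quantitative urinalysis results will be presented by visit";
- for values that the investigator judges important, "Frequency tables or listings for values classified as clinically significant by the investigator will be provided per time point if applicable".

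The general conventions in section 5 add only that "For changes from baseline, shift tables may be generated", with no time point. They also set default descriptive statistics that include the minimum and maximum, and they provide for listings of all patient data.

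**The concern.** For a patient who completes the study, two of the three post-baseline safety samples never enter the range-based table. An excursion at Week 12 or 24 that has resolved by the last sample leaves no trace there. Week 12 is the first scheduled safety sample after the up-titration window of Weeks 2 to 10 described in section 2.3, and the table uses it only if it is the patient's last.

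Safety and tolerability is among the secondary objectives in section 2.2. At stake is whether a reader of the report can see how many patients in each arm went out of range at any time on treatment, and not only how many were out of range at the end.

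**Working it through.** The SAP states no figure on this point, so there is nothing to reproduce. The check has three parts.

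**1. What the table can see.** Take a patient with a normal baseline and code each of Weeks 12, 24 and 36 as normal or out of range. There are 2 × 2 × 2 = 8 patterns, of which 7 contain at least one out-of-range value. In 3 of these 7 (Week 12 only, Week 24 only, both) the Week 36 value is normal, and the baseline-to-final table shows normal-to-normal. A worst-value table puts all 7 in an abnormal cell. This counts patterns and is not a probability. A patient low or high at baseline would appear as low-to-normal or high-to-normal, with the interim course equally hidden.

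**2. How large the loss could be.** The SAP gives no abnormality rates, so every rate here is an assumption, for patients with all three samples.

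- All abnormalities persist to the last sample: 0% missed.
- Each affected patient has one abnormality that lasts one sample and is equally likely at each of the three visits: 2/3 missed. For example, if 9 of 91 patients in an arm (10%) had one such value each, about 3 (3%) would be tabulated.
- Rate p per visit, independent between visits: the share of affected patients missed is 1 − p / (1 − (1 − p)³).

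| Assumed p | Any abnormality, 1 − (1 − p)³ | Share missed |
|---|---|---|
| 2% | 5.9% | 66% |
| 5% | 14.3% | 65% |
| 10% | 27.1% | 63% |
| 20% | 48.8% | 59% |

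The result depends on how transient the abnormalities are and when they occur. Two thirds is the top of the patterns assumed here; if transient values clustered at the earlier visits, the share would be higher.

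**3. Whether another specified output supplies the count.**

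| Output | What it shows at Weeks 12 and 24 | Out-of-range count by arm? |
|---|---|---|
| By-visit summaries (5.9.3 with section 5 defaults) | Mean change; minimum and maximum if the defaults apply | No |
| Urinalysis frequencies (5.9.3) | Categories by visit | Semi-quantitative urinalysis only |
| Clinically significant values (5.9.3) | Investigator-classified; may be only a listing | No |
| Patient listings (section 5) | Individual values | No |
| Adverse event tables (5.9.1) | Abnormalities reported as events | No |
| eGFR and albumin/creatinine ratio (5.7.2) | Mean comparison by arm | No |

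**The case against.** The strongest reply is that the SAP shows more than the shift table alone suggests. If the section 5 defaults apply to laboratory data, each arm's minimum and maximum appear at each visit, so a marked excursion would be visible. eGFR and the albumin/creatinine ratio are compared by arm at Weeks 12, 24 and 36. Urinalysis is tabulated by visit. The condition on the clinically significant output most naturally means that it is produced if such values occur. All this stands, and it narrows the gap. It does not close it: an extreme value does not say how many patients crossed a limit, and the clinically significant output rests on judgement in an open-label trial. The blinding described in section 2.3 covers the PWV evaluator and the central reader and does not mention this classification.

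Section 8.2 also places the complete list of outputs in a separate document that is not at hand. By-visit shift tables could be there. The finding is therefore limited to what the SAP itself specifies.

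Two stronger readings are tempting. A reader might infer that two of every three abnormalities will be lost, or that the final-value table is the only objective categorical laboratory display. The first holds only under assumed full transience with equal timing, and the range starts at 0%. The second overlooks the urinalysis tables and the separate output list. Nor do the documents show that the loss would differ between arms.

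The remedy has its own weakness. Three samples give three chances of an out-of-range value. With an assumed independent chance rate of 5% per sample, a worst-value table shows 1 − 0.95³ = 14.3%, against 5% for one sample. This excess cannot be presumed equal between arms once unscheduled retests count in an open-label trial.

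**Conclusion.** The point holds as a limited one. As specified, the quantitative shift tables cannot show an excursion that resolves before the final sample, and no other output specified in the SAP counts such values by arm. The share of affected patients missed lies between 0% and about two thirds under the assumed patterns, and the SAP has no data to place it within that range. A baseline-to-final table contradicts nothing in the SAP; it is simply less informative than data already held allow. The laboratory outputs in 5.9.3 are descriptive, so no test, estimate or population changes and the primary PWV analysis is unaffected. This is a minor improvement to the safety summary.

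**What to change.** In section 5.9.3:
- keep the baseline-to-final shift table;
- state whether the final value means Week 36 or the last available on-treatment value. With about 15% drop-out expected (section 2.4), the choice decides whether patients who leave early are in the table;
- add shift tables from baseline to the worst post-baseline on-treatment value, highest and lowest separately, or shift tables by visit, based on scheduled samples;
- show a version that includes unscheduled samples separately, because retesting may differ between arms.

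The cost is a few lines of SAP text and about one additional descriptive table per variable, from data and range classifications already held. If the worst-value form is chosen, a note should say that it shows more chance abnormalities than a single-visit table.
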